## SUMMARY OF MAJOR CHANGES IN SAP VERSION

SAP Version	Section # and Name	Description of Change
V2.0	5.3 Per Protocol (PP) Set	Clarified existing language for conditions/medications that affect the immune response.
V2.0	6.1 General Considerations	Clarified that all subgroups are based on eCRF entries unless otherwise stated. Added definition for Baseline SARS-CoV-2 Status and added this Baseline SARS-CoV-2 Status to Table 5, as a subgrouping factor to be used in table summaries.
V2.0	6.2.2 Demographics and Baseline Characteristics	Added 3 categorical baseline variables: Baseline SARS-CoV-2 RT-PCR Results, Elecsys Anti-SARS-CoV-2 Results, and Baseline SARS-CoV-2 Status.
V2.0	6.3.2 Unsolicited Treatment-Emergent Adverse Events	Updated to reflect only Solicited ARs that meet SAE criteria are recorded on the Reactogenicity eCRF.
V2.0	6.4.2 Immunogenicity Analysis	Updated wording in 6.4.2.2 Analytical summaries, and added a new Table 6 to clarify the covariates used in the ANCOVA analyses. Renumbered later tables and added clarifying language to Table 7. Removed bar-plot of ANCOVA-based GMT.
V3.0	6.2.4 Prior and Concomitant Medications	“Antipyretic or analgesic medication within 28 days postinjection” item removed
V3.0	6.4.2.1. Analysis of Secondary Immunogenicity Endpoints	For GMFR, values below LLOQ imputed to LLOQ
V3.0	6.4.2.2 Analytical summaries	Added D181 GMT/GMR; added figure for D181 GMFR, SCR, SRR, and GMR
V3.0	6.5.1.2 SARS-CoV-2 Infection	Asymptomatic SARS CoV 2 infection language removed
V3.0	Appendix H TEAE of Specifical Interest by SMQ	SMQ table updated
V4.0	Global update	Part 2 added to the SAP per protocol amendment 1 dated 16-Jan-2024 and protocol amendment 2 dated 14 Mar 2024
V5.0	3.6.4.1. Primary Immunogenicity Endpoints	Updated the “Covariate(s)” column in Table 14, by adding “Log-transformed baseline antibody value” for all rows.

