### **2.5.3. Per Protocol (PP) Set**

The PP Set in Part 1 consists of all participants in the FAS who comply with the injection schedule, comply with the timings of immunogenicity blood sampling to have a Baseline and at least 1 post-injection assessment at Day 29 (-7 to +14 days), have no documented infection (confirmed by RT-PCR test) of either influenza or SARS-CoV-2 on Day 1 and up to Day 29 (Day 29 immunogenicity assessment + 7 days), have no major dosing error, and have no major protocol deviations or conditions/medications that affect the immune response. The PP Set will be used as the primary analysis set for analyses of immunogenicity in Cohort A or B unless otherwise specified. Participants will be analyzed according to the group to which they were randomized.

The major dosing error ranges, available in Table 3, will be used to determine participant exclusion from the PP analysis populations:

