- Percentages of participants with seroconversion (influenza) and seroresponse (SARS-CoV-2) with the corresponding 2-sided 95% CI at each post-Baseline time point,

- Percentages of participants with a GMFR results  $\geq 2$ , and  $\geq 4$  with the corresponding 2-sided 95% CI at each post-Baseline time point.

For participants in the groups receiving mRNA-1083, mRNA-1010 or influenza injections, seroconversion rate from Baseline will be provided with a 2-sided 95% CI using the Clopper-Pearson method at each post-Baseline time point. Rate of seroconversion is defined as the proportion of participants with either a pre-vaccination HAI titer CCI and a post-vaccination HAI titer CCI or a pre-vaccination HAI titer CCI and a minimum 4-fold rise in post-vaccination HAI antibody titer.

For participants in the groups receiving mRNA-1083, mRNA-1283.222 or mRNA-1273.222, seroresponse rate will be summarized for planned post-Baseline visits, including the 2-sided 95% CI using the Clopper-Pearson method. Rate of Seroreponse for SARS-CoV-2 is defined as a  $\geq 4$  fold rise in nAb titer from Baseline in those with Baseline titer  $\geq$  LLOQ, or a post-Baseline titer  $\geq 4 \times$  LLOQ if Baseline titer is  $<$  LLOQ.

In addition, the following analysis statistics will be provided by treatment arm (available in Table 7) at Day 29 and D181 for the following influenza and SARS-CoV-2 endpoints:

- Within Treatment Group, Model-based geometric mean titer (GMT) with the corresponding 95% CI,
- Between Treatment Group, Pair-wise geometric mean ratios (GMR) with the corresponding 95% CI

The model-based GM titer will be estimated based on an analysis of covariance (ANCOVA) model, and it will be modelled separately for Cohort A and Cohort B. In the ANCOVA model, the log-transformed antibody titer at a post-Baseline timepoint (Day 29 or Day 181) are treated as a dependent variable, with the treatment group as an explanatory variable and covariates listed in Table 6 below for different assays, Cohorts and subgroups:

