**Table 6 Covariates Included in Different ANCOVA Models (Part 1)**

Assay	Cohort	Subgroup	Covariate(s)
PsVNA	A	Overall	Influenza vaccine status since Sept 2022 (IRT)
		Overall	None
	B	Prior bivalent Covid vaccine status: Received	None
		Prior bivalent Covid vaccine status: Not Received	None
		Baseline SARS-CoV2 Status: Positive	None
		Baseline SARS-CoV2 Status: Negative	None
		Overall	Age Group (IRT), Influenza vaccine status since Sept 2022 (IRT)
		Overall	Age Group (EDC)
		Age Group (EDC): $\geq 18$ to $<50$ years	None
		Age Group (EDC): $\geq 50$ to $<65$ years	None
HAI	A	Prior bivalent Covid vaccine status: Received	Age Group (IRT)
		Prior bivalent Covid vaccine status: Not Received	Age Group (IRT)
		Baseline SARS-CoV2 Status: Positive	Age Group (IRT)
		Baseline SARS-CoV2 Status: Negative	Age Group (IRT)
	B	Overall	Influenza vaccine status since Sept 2022 (IRT)
		Overall	Influenza vaccine status since Sept 2022 (EDC)
		Influenza vaccine status since Sept 2022 (EDC): Received	None
		Influenza vaccine status since Sept 2022 (EDC): Not Received	None
		Overall	Age Group (IRT), Influenza vaccine status since Sept 2022 (IRT)
		Overall	Age Group (EDC), Influenza vaccine status since Sept 2022 (EDC)
		Age Group (EDC): $\geq 18$ to $<50$ years	Influenza vaccine status since Sept 2022 (IRT)
		Age Group (EDC): $\geq 50$ to $<65$ years	Influenza vaccine status since Sept 2022 (IRT)
		Influenza vaccine status since Sept 2022 (EDC)=Y	Age Group (IRT)
		Influenza vaccine status since Sept 2022 (EDC)=N	Age Group (IRT)

The GMT will be estimated by the geometric least square mean (GLSM) from the ANCOVA model for each treatment group and corresponding 2-sided 95% CI will be provided.

For each pair of between-group comparison specified in Table 7, the GMR (ratio of GMTs) between the two treatment groups in each pair will be estimated from the ANCOVA model, with 2-sided 95% CI provided accordingly.

Additional comparisons or analysis statistics will be provided by treatment arm (available in Table 7) at Day 29 for the following influenza and SARS-CoV-2 endpoints:

- Pair-wise seroconversion rate (SCR) difference (influenza) and pair-wise seroresponse rate (SRR) difference (SARS-CoV-2) with the corresponding 95% CI

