**Table 7 Exploratory between-group Immunogenicity comparisons (Part 1)**

Influenza Cohort A								
Control Arm	Treatment Arm							
	mRNA-1010 [REDACTED] CC1 $\mu$ g	mRNA-1010 [REDACTED] CC1 $\mu$ g	mRNA-1083.1 [REDACTED] CC1 $\mu$ g	mRNA-1083.1 [REDACTED] CC1 $\mu$ g	mRNA-1083.2 [REDACTED] CC1 $\mu$ g	mRNA-1083.2 [REDACTED] CC1 $\mu$ g	mRNA-1083.2 [REDACTED] CC1 $\mu$ g	mRNA-1083.3 [REDACTED] CC1 $\mu$ g
Fluarix	X	X	X	X	X	X	X	X
Fluzone HD	X	X	X	X	X	X	X	X
mRNA-1010 [REDACTED] CC1 $\mu$ g	NA	X	X	X	X	X	X	X
mRNA-1010 [REDACTED] CC1 $\mu$ g	NA	NA	X	X	X	X	X	X

Influenza Cohort B									
Control Arm	Treatment Arm								
	mRNA-1010 CCI $\mu$ g	mRNA-1010 CCI $\mu$ g	mRNA-1083.1 CCI $\mu$ g	mRNA-1083.1 CCI $\mu$ g	mRNA-1083.1 CCI $\mu$ g	mRNA-1083.2 CCI $\mu$ g	mRNA-1083.2 CCI $\mu$ g	mRNA-1083.2 CCI $\mu$ g	mRNA-1083.3 CCI $\mu$ g
Fluarix	X	X	X	X	X	X	X	X	X
mRNA-1010 CCI $\mu$ g	NA	X	X	X	X	X	X	X	X
mRNA-1010 CCI $\mu$ g	NA	NA	X	X	X	X	X	X	X

SARS-CoV-2 Cohort A							
Control Arm	Treatment Arm						
	mRNA-1283.222 CCI $\mu$ g	mRNA-1083.1 CCI $\mu$ g	mRNA-1083.1 CCI $\mu$ g	mRNA-1083.2 CCI $\mu$ g	mRNA-1083.2 CCI $\mu$ g	mRNA-1083.2 CCI $\mu$ g	mRNA-1083.3 CCI $\mu$ g
mRNA-1273.222 CCI $\mu$ g	X	X	X	X	X	X	X
mRNA-1283.222 CCI $\mu$ g	NA	X	X	X	X	X	X

SARS-CoV-2 Cohort B							
Control Arm	Treatment Arm						
	mRNA-1283.222 CCI $\mu$ g	mRNA-1083.1 CCI $\mu$ g	mRNA-1083.1 CCI $\mu$ g	mRNA-1083.1 CCI $\mu$ g	mRNA-1083.2 CCI $\mu$ g	mRNA-1083.2 CCI $\mu$ g	mRNA-1083.2 CCI $\mu$ g
mRNA-1273.222 CCI $\mu$ g	X	X	X	X	X	X	X
mRNA-1283.222 CCI $\mu$ g	NA	X	X	X	X	X	X

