**Table 14 Covariates Included in Different ANCOVA Models (Part 2)**

Assay	Subgroup	Covariate(s)
PsVNA	Overall	Log-transformed baseline antibody value, Influenza Vaccine Status Since Sept 2023 (IRT)
	Overall	Log-transformed baseline antibody value
	Covid Vaccine Status Since Sept 2023: Received	Log-transformed baseline antibody value
	Covid Vaccine Status Since Sept 2023: Not Received	Log-transformed baseline antibody value
	Baseline SARS-CoV2 Status: Positive	Log-transformed baseline antibody value
	Baseline SARS-CoV2 Status: Negative	Log-transformed baseline antibody value
HAI	Overall	Log-transformed baseline antibody value, Influenza Vaccine Status Since Sept 2023 (IRT)
	Overall	Log-transformed baseline antibody value, Influenza Vaccine Status Since Sept 2023 (EDC)
	Influenza Vaccine Status Since Sept 2023 (EDC): Received	Log-transformed baseline antibody value
	Influenza Vaccine Status Since Sept 2023 (EDC): Not Received	Log-transformed baseline antibody value

For each pair of between-group comparison specified in Table 15, the GMR between the two treatment groups in each pair will be estimated from the ANCOVA model, with its 2-sided 95% CI provided accordingly.

Seroconversion rate (SCR) for influenza from Baseline will be summarized at Day 29 with its 2-sided 95% CI using the Clopper-Pearson method for participants in the groups receiving mRNA-1083, mRNA-1010 or Fluarix.

- SCR at Day 29 is defined as the percentage of participants with a Day 29 titer **CCI** if Baseline is **CCI** or a 4-fold or greater rise if Baseline is **CCI** in anti-HA antibodies measured by HAI assay

Seroresponse rate (SRR) for SARS-CoV-2 from Baseline will be summarized at Day 29 with its 2-sided 95% CI using the Clopper-Pearson method for participants in the groups receiving mRNA-1083, mRNA-1283.815 or mRNA-1273.815.

- SRR at Day 29 is defined as the proportion of participants with a Day 29 titer  $\geq$  4-fold if Baseline is  $\geq$  LLOQ or  $\geq 4 \times$  LLOQ if Baseline titer is  $<$  LLOQ in nAb titers measured by PsVNA.

Additional comparisons or analysis statistics will be provided by treatment arm at Day 29 for the influenza and SARS-CoV-2 endpoints. For each pair of between-group comparison specified in Table 15, the difference of seroresponse/seroconversion rate (SRR/SCR) between the two treatment groups in each pair will be provided, with its 2-sided 95% CI estimated using Miettinen-Nurminen method.

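### The Part 1 ANCOVA leaves the Day 1 titre out of all 24 models while Part 2 includes it in all 10, without explanation; the cost is precision only, in exploratory GMRs

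*SAP*

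**What the plan says.** **Part 1.** SAP 2.6.4.1 models the log titre at Day 29 or Day 181, separately for Cohorts A and B, "with the treatment group as an explanatory variable and covariates listed in Table 6 below for different assays, Cohorts and subgroups". Every Table 6 entry is either none or some combination of age group and prior-season influenza vaccination. The fullest overall entry reads "Age Group (IRT), Influenza vaccine status since Sept 2022 (IRT"). The model yields the model-based GMTs and the pairwise GMRs, which "will be provided by treatment arm (available in Table 7) at Day 29 and D181". Table 7 is titled "Exploratory between-group Immunogenicity comparisons (Part 1").

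**Part 2.** Table 14 has the log Day 1 titre in every row, for example "Log-transformed baseline antibody value, Influenza Vaccine Status Since Sept 2023 (IRT").

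**Change history.** The V5.0 entry edits the covariate "column in Table 14, by adding" the log baseline value to all rows. It gives no reason and does not mention Table 6. SAP Section 4 reports no changes from the protocol's planned analysis. Protocol 9.5.1 leaves the details of the between-group comparisons to the SAP.

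**Availability.** SAP 2.5.3 admits to the Per Protocol Set only participants who "comply with the timings of immunogenicity blood sampling to have a Baseline and at least 1 post-injection assessment at Day 29". Protocol Table 1 requires the baseline sample to be drawn before injection.

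**The concern.** A participant's Day 1 titre is usually the best single predictor of the later titre by the same assay. It is measured before injection and is already required for the primary immunogenicity set, so using it needs no new data. The sponsor adjusts for it in Part 2 with the same two assays. Leaving it out of Part 1 without explanation makes the Part 1 GMR intervals wider than necessary whenever baseline and later titres are correlated. With 50 or 52 participants planned per arm, these GMRs are Part 1's between-arm titre contrasts.

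The parts need not match. Protocol 9.6 gives each its own analysis and report, and Day 29 immunogenicity is primary in Part 2 but secondary in Part 1. The SAP does not offer that, or anything else, as the reason.

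**Working it through.** **1. Row counts.** Extraction displaces the assay and cohort labels in Table 6; the total does not depend on them.

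| Table | Rows | With Day 1 titre |
|---|---|---|
| Table 6: PsVNA A, PsVNA B, HAI A, HAI B | 6 + 8 + 4 + 6 = 24 | 0 |
| Table 14: PsVNA, HAI | 6 + 4 = 10 | 10 |

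**2. The plan's own figure.** The documents give no precision or power for a GMR. The Part 1 sample-size statement concerns adverse events: 1 − 0.96^50 = 87.0% and 1 − 0.95^50 = 92.3%, both as stated in SAP Table 2. It does not bear on titres.

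**3. Precision.** The inputs are n = 50 per arm (Cohort A, SAP 2.3.3) and two assumptions: within-arm SD of 0.4 to 0.6 log10, and correlation r = 0.3 to 0.7 between Day 1 and later log titres after any Table 6 covariates. Day 181 may sit at the low end.

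Half-width (log10) = t × SD × √(2/n) × √(1 − r²), with r = 0 for the current model.

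Current model at SD 0.5: 1.96 × 0.5 × √(2/50) = 0.196, and 10^0.196 = 1.57.

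| r | √(1 − r²) | Equivalent n per arm, 50/(1 − r²) | CI factor, SD 0.4 (now 1.44) | SD 0.5 (now 1.57) | SD 0.6 (now 1.72) |
|---|---|---|---|---|---|
| 0.3 | 0.954 | 54.9 | 1.41 | 1.54 | 1.68 |
| 0.5 | 0.866 | 66.7 | – | 1.48 | – |
| 0.7 | 0.714 | 98.0 | 1.29 | 1.38 | 1.47 |

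**4. Validity.** Simulation used 20,000 runs per setting, SD 0.5, 50 or 52 per arm, true difference zero, and only the Table 7 arms in the model. Coverage was 94.9–95.3% unadjusted and 94.8–95.2% adjusted. Width ratios were 0.955, 0.867 and 0.715, slightly above the formula because the slope is estimated. Omitting the covariate therefore does not invalidate the intervals. A chance imbalance of one standard error in mean baseline (0.5 × √(2/50) = 0.1 log10) moves an unadjusted GMR by 10^(0.1r), or 1.07 to 1.17 for r = 0.3 to 0.7, but the wider unadjusted interval already allows for that.

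**5. Which arms enter the model.** SAP 2.6.4.1 points to Table 7 but does not say which arms each model contains. Some of the 12 arms per cohort lack the antigen being assayed:
- PsVNA, Cohort A: 4 (two mRNA-1010 arms, Fluarix, Fluzone HD)
- PsVNA, Cohort B: 3 (the same without Fluzone HD)
- HAI: 2 (mRNA-1283.222, mRNA-1273.222)

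In such arms the later titre should track baseline closely. Pooling them makes a common slope too steep and the residual variance too small for the antigen arms. With r = 0.85–0.95 assumed there and all 12 arms pooled, simulated coverage for an antigen-arm contrast was:

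| Model, 12 arms | 4 no-antigen arms | 3 | 2 |
|---|---|---|---|
| Common slope | 91.0–92.8% | 92.5–93.7% | 93.4–94.3% |

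The unadjusted 12-arm model kept 94.8–95.3%. With arm-specific slopes and residual variances, coverage was 94.7–95.3% and width ratios 0.97, 0.88 and 0.73.

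**6. Size of the addition.** Assume 4 influenza and 2 SARS-CoV-2 strains, 2 visits, and one overall model per assay and cohort: 4 × 2 × 2 + 2 × 2 × 2 = 24 models. Table 7 lists 29 and 24 influenza contrasts and 13 and 13 SARS-CoV-2 contrasts: (29 + 24) × 4 × 2 + (13 + 13) × 2 × 2 = 528 GMRs. The Cohort B SARS-CoV-2 panel as extracted lacks mRNA-1083.3; with it the total is 536. Repeating every Table 6 row would take 10 × 4 × 2 + 14 × 2 × 2 = 136 models.

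**7. Timing.** Part 1 enrolled in April–May 2023 (Protocol 2). The latest Day 181 visit is 31 May 2023 + 180 + 14 days = 11 December 2023. The current SAP cites an eCRF dated 31 May 2024.

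**The case against.** The strongest reply is that nothing is wrong and the difference can be understood. The protocol sets no covariate rule, the intervals are valid, the contrasts are exploratory, and no test is planned. Protocol 9.5 requires the SAP to be final before the interim analyses, and Protocol 2.1.1 reports the Part 1 interim as complete, so leaving Table 6 alone is consistent with a frozen plan. Baseline already enters the by-arm fold rises and the seroconversion and seroresponse differences. At r = 0.3 the interval narrows by only about 5%. Phase 3 enrolment was complete by November 2023, so the result cannot affect that selection, and the Part 1 report may already be written. The under-coverage in step 5 is a risk of the remedy, not a fault of the plan.

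Most of this stands and sets the size of the point. It does not remove it. The SAP never states the freeze argument. Fold rises are planned by arm, not as between-arm contrasts, and the seroconversion and seroresponse differences dichotomise the response. Protocol 9 allows added exploratory analyses if identified in the CSR, and the documents do not show that the Part 1 report is closed. The coverage risk is a reason to name the arms, as SAP 2.6.4.1 already does for the seroresponse rate: "For participants in the groups receiving mRNA-1083, mRNA-1283.222 or mRNA-1273.222, seroresponse rate will be summarized".

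**Conclusion.** The point holds as a small, optional improvement. Table 6 omits an available pre-injection covariate that Table 14 uses throughout, and the SAP does not say why. Randomisation protects the Part 1 GMRs from systematic baseline confounding, and Per Protocol exclusions apply with or without the covariate, so only precision is lost. The same holds for the model-based GMTs from the same fits. The gain runs from about 5% narrower log-scale intervals at r = 0.3 to about 28% at r = 0.7. It rests on assumed correlations and SDs, and on fitting only the arms in the matching Table 7 panel. No test or Phase 3 decision would change.

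**What to change.** Keep the Table 6 models as the prespecified Part 1 analysis. Beside them, for the overall models with IRT strata at Day 29 and Day 181, report the same models with the log Day 1 titre added, using the same strain and assay and the 0.5 × LLOQ rule of SAP 2.6.1. Subgroup versions are optional.

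Name the arms in each added model: only those in the matching Table 7 panel. If all 12 arms are kept, allow arm-specific slopes and residual variances and evaluate each GMR at a common mean baseline.

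Label the output supplementary and added after the Part 1 interim. Record it in the SAP change log with the reason Parts 1 and 2 differ. The disclosure matters: the protocol shows only safety results from that interim, but its planned content in Protocol 9.6 included immunogenicity, so titres were probably seen too. If no models are added, the dated explanation alone would still close the documentary gap.

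The cost is one model term, a change-log entry, 24 models and about 528 further exploratory GMRs without multiplicity control. No new data are needed.

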**Table 6 Covariates Included in Different ANCOVA Models (Part 1)**

Assay	Cohort	Subgroup	Covariate(s)
PsVNA	A	Overall	Influenza vaccine status since Sept 2022 (IRT)
		Overall	None
	B	Prior bivalent Covid vaccine status: Received	None
		Prior bivalent Covid vaccine status: Not Received	None
		Baseline SARS-CoV2 Status: Positive	None
		Baseline SARS-CoV2 Status: Negative	None
		Overall	Age Group (IRT), Influenza vaccine status since Sept 2022 (IRT)
		Overall	Age Group (EDC)
		Age Group (EDC): $\geq 18$ to $<50$ years	None
		Age Group (EDC): $\geq 50$ to $<65$ years	None
HAI	A	Prior bivalent Covid vaccine status: Received	Age Group (IRT)
		Prior bivalent Covid vaccine status: Not Received	Age Group (IRT)
		Baseline SARS-CoV2 Status: Positive	Age Group (IRT)
		Baseline SARS-CoV2 Status: Negative	Age Group (IRT)
	B	Overall	Influenza vaccine status since Sept 2022 (IRT)
		Overall	Influenza vaccine status since Sept 2022 (EDC)
		Influenza vaccine status since Sept 2022 (EDC): Received	None
		Influenza vaccine status since Sept 2022 (EDC): Not Received	None
		Overall	Age Group (IRT), Influenza vaccine status since Sept 2022 (IRT)
		Overall	Age Group (EDC), Influenza vaccine status since Sept 2022 (EDC)
		Age Group (EDC): $\geq 18$ to $<50$ years	Influenza vaccine status since Sept 2022 (IRT)
		Age Group (EDC): $\geq 50$ to $<65$ years	Influenza vaccine status since Sept 2022 (IRT)
		Influenza vaccine status since Sept 2022 (EDC)=Y	Age Group (IRT)
		Influenza vaccine status since Sept 2022 (EDC)=N	Age Group (IRT)

The GMT will be estimated by the geometric least square mean (GLSM) from the ANCOVA model for each treatment group and corresponding 2-sided 95% CI will be provided.

For each pair of between-group comparison specified in Table 7, the GMR (ratio of GMTs) between the two treatment groups in each pair will be estimated from the ANCOVA model, with 2-sided 95% CI provided accordingly.

Additional comparisons or analysis statistics will be provided by treatment arm (available in Table 7) at Day 29 for the following influenza and SARS-CoV-2 endpoints:

- Pair-wise seroconversion rate (SCR) difference (influenza) and pair-wise seroresponse rate (SRR) difference (SARS-CoV-2) with the corresponding 95% CI

For each pair of between-group comparison specified in Table 7, the difference of seroresponse/seroconversion rate (SRR/SCR) between the two treatment groups in each pair at Day 29 will be provided, with 2-sided 95% CI estimated using Miettinen-Nurminen method.

A bar plot for GMR and GMFR at Day 29 and at D181, as well as a bar plot of SCR (influenza)/SRR (SARS-CoV-2) at Day 29 and D181 will be provided.

**Table 7 Exploratory between-group Immunogenicity comparisons (Part 1)**

Influenza Cohort A								
Control Arm	Treatment Arm							
	mRNA-1010 [REDACTED] CC1 $\mu$ g	mRNA-1010 [REDACTED] CC1 $\mu$ g	mRNA-1083.1 [REDACTED] CC1 $\mu$ g	mRNA-1083.1 [REDACTED] CC1 $\mu$ g	mRNA-1083.2 [REDACTED] CC1 $\mu$ g	mRNA-1083.2 [REDACTED] CC1 $\mu$ g	mRNA-1083.2 [REDACTED] CC1 $\mu$ g	mRNA-1083.3 [REDACTED] CC1 $\mu$ g
Fluarix	X	X	X	X	X	X	X	X
Fluzone HD	X	X	X	X	X	X	X	X
mRNA-1010 [REDACTED] CC1 $\mu$ g	NA	X	X	X	X	X	X	X
mRNA-1010 [REDACTED] CC1 $\mu$ g	NA	NA	X	X	X	X	X	X

Influenza Cohort B									
Control Arm	Treatment Arm								
	mRNA-1010 CCI $\mu$ g	mRNA-1010 CCI $\mu$ g	mRNA-1083.1 CCI $\mu$ g	mRNA-1083.1 CCI $\mu$ g	mRNA-1083.1 CCI $\mu$ g	mRNA-1083.2 CCI $\mu$ g	mRNA-1083.2 CCI $\mu$ g	mRNA-1083.2 CCI $\mu$ g	mRNA-1083.3 CCI $\mu$ g
Fluarix	X	X	X	X	X	X	X	X	X
mRNA-1010 CCI $\mu$ g	NA	X	X	X	X	X	X	X	X
mRNA-1010 CCI $\mu$ g	NA	NA	X	X	X	X	X	X	X

SARS-CoV-2 Cohort A							
Control Arm	Treatment Arm						
	mRNA-1283.222 CCI $\mu$ g	mRNA-1083.1 CCI $\mu$ g	mRNA-1083.1 CCI $\mu$ g	mRNA-1083.2 CCI $\mu$ g	mRNA-1083.2 CCI $\mu$ g	mRNA-1083.2 CCI $\mu$ g	mRNA-1083.3 CCI $\mu$ g
mRNA-1273.222 CCI $\mu$ g	X	X	X	X	X	X	X
mRNA-1283.222 CCI $\mu$ g	NA	X	X	X	X	X	X

SARS-CoV-2 Cohort B							
Control Arm	Treatment Arm						
	mRNA-1283.222 CCI $\mu$ g	mRNA-1083.1 CCI $\mu$ g	mRNA-1083.1 CCI $\mu$ g	mRNA-1083.1 CCI $\mu$ g	mRNA-1083.2 CCI $\mu$ g	mRNA-1083.2 CCI $\mu$ g	mRNA-1083.2 CCI $\mu$ g
mRNA-1273.222 CCI $\mu$ g	X	X	X	X	X	X	X
mRNA-1283.222 CCI $\mu$ g	NA	X	X	X	X	X	X

